2.4 Secondary Endpoints

- To determine time to progression (TTP) and progression free survival (PFS)
- To determine overall survival (OS)
- To assess Nivolumab correlative biologic studies to assess immunomonitoring of lymphocytes subsets including T and NK cell, and *ex-vivo* assessment of immune functional activities.

2.5 Safety Parameters

Infusion related and treatment emergent toxicities per National Cancer Institute Common Terminology Criteria for Adverse Events (NCI CTCAE) v4.0

3 ELIGIBILITY CRITERIA

3.1 Inclusion Criteria

- Patients must be at least 18 years of age with evidence of progression, relapse or refractory disease from last line of therapy as defined by IMWG criteria. A line of therapy is defined as one or more cycles of a planned treatment program which may be one therapy or a sequence of treatments. A new line of therapy begins when a planned course of therapy is modified due to disease progression, relapse or toxicity or when a planned period of observation off therapy.
Measurable disease as defined by any of the following:
 - Serum M-protein ≥ 0.5 g/dl (≥ 10 g/l)
 - Urine monoclonal protein ≥ 200 mg/24h
 - Involved FLC level ≥ 10 mg/dl (≥ 100 mg/l) and an abnormal serum free light chain ratio (<0.26 , or >1.65)
 - Measurable biopsy proven plasmacytoma (should be measured within 28 days of initial investigational agent dosing)
- Patients must have exhausted all available therapies known to provide clinical benefit and has progressed, relapsed or is refractory to last line of treatment.
- Patients must have had at least 4 prior lines of therapy.
- Patient may be enrolled at any time from last line of therapy.
- Patients must have ANC $> 1000/\mu\text{L}$; Platelets $\geq 75,000/\mu\text{L}$, if plasma cell percentage on bone marrow biopsy aspirate or core is $> 30\%$, platelet eligibility requirement will be adjusted to $60,000/\mu\text{L}$.
- Patients must have adequate hepatic function as evidenced by: total bilirubin ≤ 1.5 mg/dL, alkaline phosphatase $\leq 3X$ the ULN, AST/ALT $\leq 2X$ the ULN
- Patients must have adequate renal function as evidenced by serum creatinine ≤ 2 mg/dL or calculated creatinine clearance of ≥ 40 ml/min within 14 days of registration using MDRD formula.
- Patient must be able to swallow capsule or tablet.
- Patients must provide informed consent.
- Patients must have a left ventricular ejection fraction $\geq 30\%$, no uncontrolled arrhythmias or New York Heart Association class III-IV heart failure.
- Patients must have a Karnofsky performance status ≥ 70 .
- A negative pregnancy test will be required for all women of child bearing potential. Breast feeding is not permitted.
- Fertility requirements
 - Female patients with child bearing potential must have a negative pregnancy test at least 7 days before starting treatment drugs.
 - Male patients must agree to use an adequate method of contraception for the duration of the study and for 7 months afterwards.
 - Female patients must be either post-menopausal, free from menses ≥ 2 yrs, surgically sterilized, willing to use two adequate barrier methods of contraception to prevent pregnancy, or agree to abstain from sexual activity starting from screening and for 5 months afterwards.

- Female patients of child bearing potential must agree to comply with the fertility and pregnancy test requirements dictated by the Rev-Assist program.\

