	
Measurable biopsy proven plasmacytoma (should be measured within 28 days of initial investigational agent dosing)
 
 Patients must have exhausted all available therapies known to provide clinical benefit and has progressed, relapsed or is refractory to last line of treatment. Patients must have had at least 4 prior lines of therapy. Patient may be enrolled at any time from last line of therapy Patients must have ANC > 1000/μL; Platelets \geq75,000/μL, if plasma cell percentage on bone marrow biopsy aspirate or core is > 30%, platelet eligibility requirement will be adjusted to 60,000/μl. Patients must have adequate hepatic function as evidenced by: total bilirubin \leq 1.5 mg/dL, alkaline phosphatase \leq 3X the ULN, AST/ALT \leq 2X the ULN Patients must have adequate renal function as evidenced by serum creatinine \leq 2mg/dL or calculated creatinine clearance of \geq 40ml/min within 14 days of registration using MDRD formula. Patient must be able to swallow capsule or tablet. Patients must provide informed consent. Patients must have a left ventricular ejection fraction \geq 30%, no uncontrolled arrhythmias or New York Heart Association class III-IV heart failure. Patients must have a Karnofsky performance status \geq 70. A negative pregnancy test will be required for all women of child bearing potential. Breast feeding is not permitted. Fertility requirements 
 Female patients with child bearing potential must have a negative pregnancy test at least 7 days before starting treatment drugs. Male patients must agree to use an adequate method of contraception for the duration of the study and for 7 months afterwards. Female patients must be either post-menopausal, free from menses \geq2 yrs, surgically sterilized, willing to use two adequate barrier methods of contraception to prevent pregnancy, or agree to abstain from sexual activity starting from screening and for 5 months afterwards. Female patients of child bearing potential must agree to comply with the fertility and pregnancy test requirements dictated by the Rev-Assist program.
--	--

Exclusion Criteria

- Patients with peripheral neuropathy > CTCAE grade 2
- Patients receiving concurrent corticosteroids at the time protocol therapy is initiated other than for physiologic maintenance treatment.
- History of allergic reaction (including erythema nodosum) to lenalidomide

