3.2 Exclusion Criteria

- Patients with peripheral neuropathy > CTCAE grade 2
- Patients receiving concurrent corticosteroids at the time protocol therapy is initiated other than for physiologic maintenance treatment.
- History of allergic reaction (including erythema nodosum) to lenalidomide
- Concurrent use of complementary or alternative medicines that would confound the interpretation of toxicities and antitumor activity of the study drugs.
- Patients with contraindication to thromboprophylaxis.
- Unacceptable cardiac risk factors defined by any of the following criteria: Patients with congenital long QT syndrome, any history of ventricular fibrillation or torsade de pointes, bradycardia defined as HR< 50 bpm, Left ventricular ejection fraction < 30%
- Patients who have received targeted or investigational agents within 2 weeks or within 5 half-lives of the agent and active metabolites (whichever is longer) and who have not recovered from side effects of those therapies.
- Patients who have undergone major surgery ≤ 2 weeks prior to starting study drug or who have not recovered from the side-effects of surgery.
- Patients with known positivity for human immunodeficiency virus (HIV), or hepatitis C. Baseline testing for HIV and hepatitis C is not required
- Patients with a history of another primary malignancy that is currently clinically significant or currently requires active intervention, other than non- melanoma skin cancer and carcinoma in situ of the cervix should not be enrolled. Patients are not considered to have a “currently active” malignancy if they have completed therapy for a prior malignancy, are disease free from a prior malignancy for ≥ 5 yrs and are considered by their physician to be less than 30% risk of relapse.
- Patients with active (untreated or relapsed) CNS metastasis of the patient’s myeloma.
- Patients with a history of gastrointestinal surgery or other procedure that might, in the opinion of the investigator(s), interfere with the absorption or swallowing of the study drugs.
- Patients with any significant history of non-compliance to medical regimens or unwilling or unable to comply with the instructions given to them by the study staff.
- Any other medical condition, including mental illness or substance abuse, deemed by the investigator(s) to likely interfere with the patient’s ability to sign informed consent, cooperate and participate in the study, or interfere with the interpretation of the results.

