6.4 Lenalidomide (RevlimidTM)

6.4.1 Lenalidomide Administration and Schedule

Lenalidomide will be given orally. The starting dose is 25 mg days 1-21 of a 28 day cycle. If a dose is missed or vomited up, the dose will not be made up. Lenalidomide doses may be consumed at any time during a dosing day without being considered 'delayed' or 'missed.'

In the event of a dose hold due to toxicity, the patient's treatment will be considered delayed and not missed.

Beginning on day 1 of cycle #2 and on day 1 of every cycle thereafter, while all conditions below have been met, patients will be evaluated for lenalidomide dose reduction.

For patients that:

- Never had a lenalidomide dose reduction due to a toxicity that was probable or definitely related to lenalidomide.
- Maintained platelet count $\geq 50,000$ at all times in the previous cycle
- Minimum ANC $\geq 1,000$ at all times in the previous cycle
- No clinically significant grade 2 or greater non-hematologic toxicities in the previous cycle

If all conditions are met, no dose reduction will occur. If any of the above conditions is not met, the patient's dose for lenalidomide will be reduced by 5 mg.

Per lenalidomide prescribing information, the starting dose of lenalidomide for patients enrolled with creatinine clearance (Clcr) < 50 mL/min will be 10mg days 1-21 of a 28 day cycle.

Dose reductions are not permanent. Lenalidomide may be increased again per treating physician discretion. In the event a patient is dose reduced to 0mg, patient may continue on study, and may still receive Nivolumab as scheduled.

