6.4.2 Lenalidomide dose levels

Before each drug dose, the patient will be evaluated for possible toxicities that may have occurred after the previous dose(s). Toxicities are to be assessed according to the NCI Common Terminology Criteria

for Adverse Events (CTCAE), Version 4.0. Dose modifications or delays will be done based on the toxicity experienced during a cycle of therapy or newly encountered on day one of a cycle.

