6.5.1 Table 6.5.1 Adverse events and Dose Adjustment of drugs

Neutropenia	Grade 3 or greater on day 1 of cycle: delay and monitor CBC weekly; if resolves to \leq grade 2 within 4 weeks, resume lenalidomide with 5mg dose reduction. If grade 3 or greater during a cycle, hold lenalidomide for the remainder of the cycle. Resume with 5mg dose reduction for subsequent cycles. G-CSF or GM-CSF are not to be used to avoid dose reductions but can be used for treatment of febrile neutropenia
Febrile Neutropenia	Hold lenalidomide for the remainder of the cycle. Consider G-CSF administration until there is adequate count recovery $ANC \geq 1000/\mu L$ + absence of fever. If neutropenia resolves \leq grade 2, resume lenalidomide at 5 mg dose reduction for subsequent cycles.
Thrombocytopenia	If grade 3 or greater, hold lenalidomide for the remainder of the cycle and until platelets $\geq 50,000/\mu L$. Then resume lenalidomide at 5 mg dose reduction for subsequent cycles.
Anemia	For grade 3 or greater, hold lenalidomide for the remainder of the cycle and until hemoglobin recovers to \leq grade 2.
Fatigue (asthenia, malaise) Lenalidomide or dexamethasone	For intolerable grade 2 or grade 3-4, hold the protocol therapy thought to be probable or definitely related to the reaction until resolves to \leq grade 1, then resume protocol therapy with dose reduction of implicated protocol therapy by one dose level (5 mg for lenalidomide and/or 50% for dexamethasone).
Rash Lenalidomide	If grade 3 or greater, hold lenalidomide until resolves to \leq grade 2, then resume protocol therapy. In the instance of intolerable recurrent rash, stop implicated drug but may continue on study.
Renal insufficiency	For patients with calculated or measured GFR $<30\text{ml/min}$, lenalidomide should be held until creatinine returns to baseline. If the calculated or measured GFR falls under 50 ml/min, the dose of lenalidomide will be reduced to 10mg if the patient began therapy with 25mg dosage.
Venous Thromboembolism	All protocol should be held until the patient is adequately anti-coagulated. Patients with recurrent thrombosis despite adequate anti-coagulation should be removed from protocol therapy.

Suspected Pregnancy	Protocol therapy should be held until pregnancy is ruled out. Discontinue all protocol therapy if pregnancy is positive

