6.9.6 Study Calendar Schedule of Events

Investigations	Screening	C1D1 ^a	C1D15 ^a	C2D1 ^a	C2D15 ^a	CxD1 ^a	CxD15 ^a	C12D1 ^a	Off study ^b
History, physical examination, concomitant medication review	X	X		X		X		X	X
Informed written consent	X								
Confirmation of disease relapse and prior treatment	X								
Skeletal survey (CT or MRI as clinically indicated) ^c	X								X
MUGA or ECHO	X								
β-hCG ^d	X								
Toxicity evaluation	X	X		X		X	X		X
CBC / differential / platelets ^e	X	X	X	X	X	X	X ^f		X ^f
PTT, INR, TSH ^e	X								
BMP, glucose, magnesium ^e	X	X		X		X	X		
LFTs	X	X		X		X	X		
Beta 2 microglobulin ^g	X								X
12-lead ECG ^h	X								
Serum monoclonal protein assessments ⁱ	X	X ⁱ		X ⁱ		X ⁱ			X ⁱ
24hr urine for creatinine clearance	X								
24hr urine monoclonal protein and immunofixation ^j	X	X ^j		X ^j		X ^j	X		X ^j
BM biopsy, unilateral ^k	X						X ^k		X ^k
nivolumab Given		X	X	X	X	X	X	X	

Prescribe lenalidomide via RevAssist ^l	X								
Dexamethasone ^m	X								
Pregnancy test ⁿ	X								
Correlative studies, peripheral blood ^o		X ^o	X	X	X	X	X	X	X
Correlative studies, bone marrow aspirate ^q	X					X ^q			X
Monitoring ^p	X								

- a. Time points in the preceding table have a +/- 4 day window to accommodate weekends, holidays, and for patient convenience.
- b. Off study correlates will be done. In addition, continued T-cell correlate will be done at 1,3, and 6 months after removal from study
- c. Skeletal survey will be done at baseline and may be done at evidence of progression of disease. CT scan will be done to document size of plasmacytoma if this is the only measurable disease.
- d. Female patients of childbearing potential (FCBP, defined in section 8.5) must have a negative pregnancy test (β -hCG) as required by the RevAssist program.
- e. CBC d/p will be monitored biweekly in cycles 1 to 4, then monthly thereafter. Chemistry tests, including electrolytes, glucose and serum creatinine, should be performed every 2 weeks during the first 2 months of therapy and once a month thereafter. Serum electrolyte monitoring should include potassium, magnesium and calcium. PTT, INR and TSH will be checked every 2 months.
- f. Starting C5D1, CBC will be done monthly on D1 of each cycle.
- g. Beta 2 microglobulin will be done after every 2 cycles and at evidence of progression of disease.

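### The renal entry rule has no GFR floor for patients with creatinine up to 2 mg/dL, so a patient can enrol below 30 ml/min, where the lenalidomide start and hold rules conflict.

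*Combined protocol and SAP*

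**What the plan says.** **Entry.** Section 3.1 and the synopsis give two alternative routes to adequate renal function: serum creatinine up to 2 "mg/dL or calculated creatinine clearance of" at least 40 ml/min, assessed "within 14 days of registration using MDRD formula". Section 3.2 has no renal exclusion. Its catch-all clause reaches "Any other medical condition, including mental illness or substance abuse, deemed by the investigator(s) to likely interfere with" consent, participation or interpretation of the results, and it names no renal level. The study calendar (6.9.6) lists "24hr urine for creatinine clearance" at screening, with no threshold attached.

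**Starting dose.** Section 6.4.1 starts patients enrolled with clearance below 50 mL/min at 10 mg on days 1-21, and attributes this to the prescribing information. The band has no lower end.

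**Hold.** For a calculated or measured GFR below 30 ml/min, Table 6.5.1 says "lenalidomide should be held until creatinine returns to baseline". Its next sentence lowers the dose to 10 mg when GFR falls under 50 in a patient who began at 25 mg. Section 6.4.2 makes dose changes "based on the toxicity experienced during a cycle of therapy or newly encountered on day one of a cycle".

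**New cycles.** The conditions in section 6.7 cover neutrophils, platelets and lenalidomide-related adverse events. None concerns creatinine or GFR.

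**The concern.** The protocol uses 30 ml/min as the level at which lenalidomide is withheld, but its entry rule does not use that level. A patient can therefore be eligible, be assigned 10 mg, and already be under the hold level on the first day. The site then has two instructions that do not fit together.

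This is a safety matter because section 9.2 states that about two-thirds of lenalidomide leaves the body unchanged in urine. At stake is consistent handling of these patients across sites. The response analysis and the decision rule are not at stake.

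**Working it through.** The plan states no figure to reproduce here. The check is first one of logic, then of whether the gap can be reached in practice.

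**1. The rules applied to one patient: creatinine at or below 2 mg/dL, stable GFR below 30 ml/min**

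- Entry (3.1, synopsis): admitted on creatinine alone.
- Exclusion (3.2): no renal criterion applies.
- Start (6.4.1): 10 mg, since clearance is below 50.
- Hold (Table 6.5.1): triggered by GFR below 30, released when creatinine is at baseline. It is at baseline already.

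There are two ways to read the hold. If it covers only decline on study, this patient receives 10 mg at a GFR at which another patient's drug would be withheld. If it applies from cycle 1 day 1, it contradicts the 10 mg start, and its release condition is met at once. So it either gives this patient no protection or cannot be applied coherently.

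**2. Can the gap be reached under MDRD?**

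The protocol names MDRD but prints no equation. Assumed form:

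GFR = k × Scr^-1.154 × age^-0.203 × 0.742 (women) × 1.212 (race term, if used), with k = 175 or 186 and ages 45 to 85. The result is compared directly with the protocol's ml/min levels.

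Example, woman aged 65, creatinine 2.0, k = 175, no race term: 175 × 0.4494 × 0.4285 × 0.742 = 25.0.

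GFR at creatinine 2.0 mg/dL, age 45 to age 85:

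| Version | Women | Men |
|---|---|---|
| 175, no race term | 26.9 to 23.7 | 36.3 to 31.9 |
| 186, no race term | 28.6 to 25.2 | 38.6 to 33.9 |
| 175, race term | 32.7 to 28.7 (below 30 from age 69) | 44.0 to 38.7 |
| 186, race term | 34.7 to 30.5 (none below 30) | 46.8 to 41.1 |

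Creatinine at which a woman's GFR equals 30, no race term: Scr = (k × age^-0.203 × 0.742 / 30)^(1/1.154). This gives 1.82 (age 45) to 1.63 (age 85) with k = 175, and 1.92 to 1.72 with k = 186. Above these values and up to 2.0, she is eligible with a GFR below 30.

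**3. Does the 40 ml/min limb do any work for women?**

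Replacing 30 by 40, and including the race term where used, the matching creatinine for women aged 45 to 85 runs from 1.27 to 1.77 across all four versions. It is always under 2.0. Any woman in that range with GFR of at least 40 already passes on creatinine, so the second limb never decides her entry.

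**4. Sensitivity to the formula**

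Cockcroft-Gault (assumed; weights also assumed): (140 − age) × weight / (72 × Scr), × 0.85 for women. At creatinine 2.0:

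- Man, 80 years, 70 kg: 60 × 70 / 144 = 29.2.
- Man, 75 years, 70 kg: 65 × 70 / 144 = 31.6.
- Woman, 75 years, 60 kg: 65 × 60 / 144 × 0.85 = 23.0.

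The finding that no man falls below 30 therefore holds only under MDRD.

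**The case against.** **The hold may apply from day 1.** The 30 ml/min sentence in Table 6.5.1 has no onset condition, whereas the next sentence speaks of GFR falling under 50. Section 6.4.2 calls for an evaluation before each dose, and section 6.4.1 lets a patient at 0 mg stay on study with nivolumab. This has force: the text does not settle that the hold is confined to on-study decline. A reader might infer that the protocol plainly directs dosing below its hold level. The documents do not go that far. They show rules that conflict, and the release condition fails on either reading.

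**Harm is not shown.** A reader might also infer that 10 mg at a stable GFR below 30 is unsafe. The documents do not establish this. Section 6.4.1 already cuts the dose from 25 mg to 10 mg, and the prescribing information it cites is not available here. This objection stands.

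**Other safeguards exist.** Chemistry is checked every two weeks for the first two months and blood counts biweekly in cycles 1 to 4. Lenalidomide is held for grade 3 or greater cytopenias. When the section 6.4.1 conditions on counts or toxicity are not met, the "dose for lenalidomide will be reduced by 5 mg". Subsite eligibility is verified centrally (section 4), and a patient can be withdrawn for welfare (6.8). These lower the risk, but most act after exposure and none sets a floor.

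**A clarification would do, without excluding anyone.** A sentence in 6.4.1 or Table 6.5.1 could resolve the conflict and keep these patients, who have exhausted other therapies. That is a legitimate alternative if the clinicians judge 10 mg acceptable below 30.

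**Conclusion.** The concern holds as a minor inconsistency between the entry, start and hold rules. The missing floor follows from the text alone. The calculations show only that it can be reached.

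Under the assumed MDRD coefficients, the patients affected are mainly women with creatinine from about 1.6-1.9 up to 2.0 mg/dL. With constant 186 and the race term, nobody aged 45 to 85 is affected. Under Cockcroft-Gault some older or lighter men are affected too. The documents give no frequency, so the number expected among 18 patients cannot be stated.

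No effect on the sample size, the response thresholds or the decision rule should be inferred, since none of them depends on the renal criterion. Confidence is medium: the equations, ages and weights are assumptions, and the clinical meaning of a stable GFR below 30 is outside the documents.

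**What to change.** In section 3.1 and the synopsis, change the renal criterion to: serum creatinine ≤2 mg/dL and calculated GFR (MDRD) ≥30 ml/min, or calculated clearance (MDRD) ≥40 ml/min, within 14 days of registration. The sponsor's clinicians should confirm the 30 ml/min level. The start rule in 6.4.1 and the hold in Table 6.5.1 can stay as they are, because a patient admitted under this rule would have a baseline MDRD GFR at or above the hold level.

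**Cost.** A wording amendment in two places. No new test is needed, since MDRD is already the named formula and chemistry is already collected at screening. A few patients with poor renal function become ineligible: under the assumed coefficients without the race term, women above creatinine of about 1.63 to 1.92 mg/dL, depending on age and constant, and no man aged 45 to 85 with creatinine up to 2.0.

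**Limit.** The floor is defined by MDRD. A patient whose measured or Cockcroft-Gault value is below 30 while MDRD is above it could still enter, so the clinicians should consider this when they confirm the threshold.

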9.2 LENALIDOMIDE (Revlimid™)

Lenalidomide (REVLIMID®), a thalidomide analogue, is an immunomodulatory agent with anti-angiogenic properties. The chemical name is 3-(4-amino-1-oxo 1, 3-dihydro -2H-isoindol-2-yl) piperidine-2, 6-dione. Lenalidomide has been studied extensively in myeloma and it is approved for use in newly diagnosed and in relapsed MM.

Supply: REVIMID® (lenalidomide) is available in 5, 10, 15 and 25 mg capsules for oral administration. Each capsule contains lenalidomide as the active ingredient and the following inactive ingredients: lactose anhydrous, microcrystalline cellulose, croscarmellose sodium, and magnesium stearate. The 5 mg capsule shell contains gelatin, titanium dioxide and black ink. The 10 mg capsule shell contains gelatin, FD&C blue #2, yellow iron oxide, titanium dioxide and black ink.

Elimination: The metabolic profile of lenalidomide in humans has not been studied. In healthy volunteers, approximately two-thirds of lenalidomide is eliminated unchanged through urinary excretion. The process exceeds the glomerular filtration rate and therefore is partially or entirely active. Half-life of elimination is approximately 3 hours.

Pregnancy: Due to its structural similarities to thalidomide, a known human teratogen, lenalidomide is contraindicated in pregnant women and women capable of becoming pregnant. When there is no alternative, females of childbearing potential may be treated with lenalidomide provided adequate precautions are taken to avoid pregnancy. Females must commit either to abstain continuously from heterosexual sexual intercourse or to use two methods of reliable birth control, including at least one

highly effective method (e.g., IUD, hormonal contraception, tubal ligation, or partner's vasectomy) and one additional effective method (e.g., latex condom, diaphragm, or cervical cap), beginning 4 weeks prior to initiating treatment with REVCLIMID® (lenalidomide), during therapy with REVCLIMID® (lenalidomide), during therapy delay, and continuing for 4 weeks following discontinuation of REVCLIMID® (lenalidomide) therapy. If hormonal or IUD contraception is medically contraindicated, two other effective or highly effective methods may be used.

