10.5 Pregnancy Statement and Use in Nursing Women

All women of childbearing potential MUST have a negative pregnancy test as required by the RevAssist program. If the pregnancy test is positive, the patient must not receive any investigational product and must not be enrolled in the study.

If, following initiation of the investigational product, it is subsequently discovered that a study subject is pregnant or may have been pregnant at the time of investigational product exposure, including during at least 6 half lives after product administration, the investigational product will be permanently discontinued in an appropriate manner (eg, dose tapering if necessary for subject safety).

The investigator must immediately notify Worldwide Safety @BMS of this event via the Pregnancy Surveillance Form in accordance with SAE reporting procedures. Follow-up information regarding the course of the pregnancy, including perinatal and neonatal outcome and, where applicable, offspring information must be reported on the Pregnancy Surveillance Form [provided upon request from BMS] any pregnancy that occurs in a female partner of a male study participant should be reported to BMS. Information on this pregnancy will be collected on the Pregnancy Surveillance Form.

Definition of Childbearing Potential: For the purposes of this study, a female of childbearing potential is a sexually mature female who: 1) has not undergone a hysterectomy (the surgical removal of the uterus) or bilateral oophorectomy (the surgical removal of both ovaries) or 2) has not been naturally postmenopausal for at least 24 consecutive months (i.e., has had menses at any time during the preceding 24 consecutive months).

Thalidomide, an analog of lenalidomide causes fetal harm and birth defects when administered to a pregnant woman. There are, however no adequate and well-controlled studies of lenalidomide in pregnant women. In New Zealand white rabbits at 10 and 20 mg/kg/day, lenalidomide was maternally toxic (reduced body weight gain and feed consumption; at 20 mg/kg/day, weight loss and one abortion). Developmental toxicity at 10 and 20 mg/kg/day included reduced fetal body weights and increased post implantation losses and fetal variations (morbidity/purple-discolored skin, undeveloped intermediate lung lobe, irregular nasal-frontal suture, and delayed metacarpal ossification)⁴⁵. The maternal and developmental no observed adverse effect levels (NOAELs) was 3mg/kg/day.

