16.7 Confidentiality

It is the responsibility of the investigator to ensure that the confidentiality of all patients participating in the trial and all of their medical information is maintained. Case report forms must never contain the name of a trial patient. All case report forms and any identifying information must be kept in a secure location with access limited to the study staff directly participating in the trial. Personal medical information may be reviewed by a representative of BMS, of the IRB, or of regulatory authorities in the course of auditing the trial. Every reasonable effort will be made to maintain such information as confidential.

17 Appendix. REV-ASSIST GUIDELINES

As of 11-Sep-2008,

Initial prescription process (for all patients unless otherwise noted)

1. For females of childbearing potential, obtain two negative pregnancy tests sensitive to at least 50 mIU/mL even if continuous abstinence is the chosen method of birth control. One test must be obtained within 10–14 days and one test within 24 hours prior to writing an initial prescription of REVCLIMID® (lenalidomide).
2. Obtain a baseline Complete Blood Count
3. Provide mandatory counseling: no drug sharing, no blood or sperm donation, and appropriate contraceptive
4. Complete, print, and sign REVCLIMID® Patient-Physician Agreement Form
 - **Males (adults and children)**
 - **Females of childbearing potential include females who have not undergone a natural menopause** for at least 24 consecutive months
 - **Females not of childbearing potential include females who have been postmenopausal naturally** for at least 24 consecutive months, or had a hysterectomy, or a bilateral oophorectomy
5. Fax completed and signed REVCLIMID® Patient-Physician Agreement Form to [name]
6. Instruct patient to complete phone survey by calling [name] prior to prescriber obtaining an authorization number
 - **All males:** REVCLIMID® Patient-Physician Agreement Form is considered the initial phone survey
 - **All females:** Complete the appropriate phone survey
7. Complete a prescriber phone survey for all patients by calling [name] and obtain a new authorization number for each prescription
 - You will need to enter the following information:
 - Prescriber's DEA number or Social Security number
 - Patient's Social Security number
 - Date and result of patient's pregnancy test(s) (if applicable); valid only for 7 days
 - Daily dose

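### The female contraception criterion in section 3.1 and the synopsis conflicts with sections 9.2 and 10.5: it admits some women whom 9.2 does not and, read literally, shuts out others who meet 9.2

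*Combined protocol and SAP*

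**What the plan says.** Section 3.1 (Fertility requirements) and the synopsis carry the same female bullet. A woman must be post-menopausal or free from menses for at least 2 years, or be "surgically sterilized, willing to use two adequate barrier methods of contraception to prevent pregnancy", or agree to abstain. The last option is followed by a period that starts at screening and runs for 5 months after an unnamed event. A separate bullet requires women of childbearing potential to comply with Rev-Assist.

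Section 9.2 requires continuous abstinence or two methods, of which at least one is a "highly effective method (e.g., IUD, hormonal contraception, tubal ligation, or partner's vasectomy) and one additional effective method"; its examples of the latter are condom, diaphragm and cap. There is one exception: "If hormonal or IUD contraception is medically contraindicated, two other effective or highly effective methods may be used". The commitment applies "beginning 4 weeks prior to initiating treatment", throughout therapy, and "during therapy delay, and continuing for 4 weeks following discontinuation of" lenalidomide.

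Section 10.5 defines childbearing potential for this study. It covers a sexually mature woman who "has not undergone a hysterectomy (the surgical removal of the uterus) or bilateral oophorectomy (the surgical removal of both ovaries") or who "has not been naturally postmenopausal for at least 24 consecutive months". Appendix 17 describes women not of childbearing potential as naturally postmenopausal "for at least 24 consecutive months, or had a hysterectomy, or a bilateral oophorectomy". Note d of the study calendar (6.9.6) sends the reader to section 8.5 for this definition, but 8.5 is the monocyte correlative section.

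**The concern.** The bullet and 9.2 govern the same women and differ on two things: which methods are acceptable, and which surgery removes the need for contraception. Section 9.2 is more than drug background. It is worded as an obligation and makes treatment of women of childbearing potential conditional on adequate precautions, for a drug that the protocol contraindicates in pregnancy.

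The literal wording matters. Section 4 requires subsites to submit source documents for every criterion and has eligibility verified centrally. Section 16.2 bars deviations without an approved amendment, except to remove an immediate hazard. A site applying the bullet as printed can record a woman as meeting it when her contraception falls short of 9.2, and can turn away a woman whose contraception satisfies 9.2.

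**Working it through.** The plan gives no figure to reproduce here. The check applies both rules to the same cases, using the method examples in 9.2. No contraindication to hormonal or IUD contraception is assumed unless stated.

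| Woman | Bullet in 3.1 and synopsis | 9.2 with 10.5 | Result |
|---|---|---|---|
| Hysterectomy or bilateral oophorectomy | Passes as surgically sterilised | Not of childbearing potential | Agree |
| Continuous abstinence | Passes | Passes | Agree |
| Condom + diaphragm | Passes (two barriers) | Fails: no highly effective method | Bullet too loose |
| Condom + diaphragm, hormonal or IUD use contraindicated | Passes | Passes by the exception | Agree |
| Tubal ligation alone | Passes on the ordinary meaning of sterilised | Fails: one method of the two required | Bullet too loose |
| Tubal ligation + condom | Passes | Passes | Agree |
| IUD + condom | Matches no option: one barrier only | Passes | Bullet too strict |
| IUD + condom + diaphragm | Passes (two barriers) | Passes | Agree |

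**Sterilisation.** Section 3.1 does not define the term. Section 9.2 lists tubal ligation as a contraceptive method, and 10.5 and Appendix 17 name only hysterectomy and bilateral oophorectomy as surgical exemptions. A woman with a ligation therefore remains of childbearing potential and still needs a second method.

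**Wording of the exemption.** The definition in 10.5 joins two negatives with *or*, so it could be read as requiring both surgery and menopause before a woman is exempt. Appendix 17 states the three exemptions as alternatives, which is the clearer form to adopt.

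**Timing.** Section 9.2 asks for 4 weeks = 28 days before treatment. If the bullet's start at screening applies to every option, and screening means the screening tests, section 6.9.1 lets those tests fall L days before dosing with 0 ≤ L ≤ 28. The shortfall is then 28 − L, from 0 to 28 days, assuming no contraception before screening and no deferred dose. On other readings there is none: the phrase may qualify abstinence only, which leaves 9.2 to set the start for other methods, and 6.9.1 exempts consent from the 4-week window, so screening counted from consent may open earlier. After treatment the bullet's 5 months is longer than the 4 weeks in 9.2, although the event it runs from is not named.

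**The case against.** The strongest reply is that the criteria are cumulative. The Rev-Assist bullet is itself an entry criterion, 10.5 keeps a woman with a tubal ligation within it, and calendar note l requires lenalidomide to be prescribed through that program. Section 9.2 also binds in its own right. This largely stands. A reader might infer that women could be dosed on inadequate contraception; the documents do not support that, because these safeguards should stop the two-barrier or ligation-only user before the first dose.

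The reply does not help the IUD-plus-condom user. A further requirement cannot make her match a closed list. It is fair to add that she could satisfy both rules by agreeing to a second barrier, so her exclusion depends on a literal reading.

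Three other inferences should be resisted:

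- Appendix 17 names no class of method, which might suggest that Rev-Assist has no such rule. The appendix is a process outline and the full program is not in these documents, so its silence shows nothing either way.
- The start at screening might be taken as a proven breach of the 4-week lead-in. It is only possible, for the reasons given under timing, and section 4 provides for treatment delays to be discussed, so the first dose can be put back.
- One could count the combinations of methods that conflict. Section 9.2 gives its methods as examples, so such a count would measure neither frequency nor risk.

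**Conclusion.** The conflict is real on method and on who is exempt. Two-barrier use without a contraindication, and tubal ligation alone, pass the bullet and breach 9.2; IUD plus condom meets 9.2 and, read literally, matches no option in the bullet. A timing shortfall is possible but not shown.

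The consequence is limited to eligibility and to the clarity of a safety rule. It does not affect the response endpoint, the sample size of 18 or the error rates. The documents do not say how many of the 18 will be women of childbearing potential, so any number from 0 to 18 is compatible with them; that there will be few is an assumption. The finding also rests on the ordinary meaning of surgical sterilisation and on treating the bullet as a closed list. It should be corrected because the entry criterion contradicts the protocol's own condition for using lenalidomide, and the remedy uses text already in the protocol.

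**What to change.** In section 3.1 and the synopsis, replace the options in the female bullet with two alternatives:

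1. The woman is not of childbearing potential under 10.5, stated as any one of hysterectomy, bilateral oophorectomy, or natural menopause of at least 24 consecutive months.
2. Otherwise she commits to the 9.2 rule: continuous abstinence from heterosexual intercourse, or at least one highly effective plus one additional effective method. Two other methods, effective or highly effective, are acceptable only where hormonal or IUD contraception is medically contraindicated. The commitment runs from 4 weeks before the first lenalidomide dose, through therapy and any delays, to 4 weeks after the last lenalidomide dose.

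Keep the existing 5-month period, with the sponsor stating what it runs from; the documents do not settle this. Keep the Rev-Assist bullet. Correct calendar note d to refer to 10.5 in place of 8.5.

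The cost is an amendment to one bullet in two places and one cross-reference. A few women may start later because of the lead-in that 9.2 already requires, and any screening test that then falls outside the 4-week window in 6.9.1 would need repeating.
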